The Effect of Early Prone Position on Prognosis in
Acute Respiratory Failure Due to COVID-19
Pneumonia

05.06.2020

Our study was planned retrospectively in 5 Covid Cohort intensive care units in our hospital to include the dates 15.03.2020 / 15.05.2020. The study started after getting approval from the local ethics committee of our hospital, ethics committee of the Ministry of Health and registering to Clinical Trials. Written and verbal consent was obtained from the patients themselves and / or their legal heirs.

The data of patients over 18 years old who were followed up and treated in the intensive care unit due to acute respiratory failure due to Covid 19 pneumonia were retrospectively reviewed.

Patients who developed acute respiratory failure due to Covid-19 pneumonia and received conventional oxygen therapy with reservoir mask oxygen at the stage of admission to the intensive care unit were included in the study.

patients with respiratory acidosis ($\text{pH} < 7,30$ and $\text{PaCO}_2 > 50$ mmhg), P / F ratio below 150, Glaskow Coma Score (GKS) below 12 points, hemodynamic instability, primary pulmonary pathologies other than pneumonia (lung cancer, cardiopulmonary edema, carcinogen syndrome, etc.) were excluded. patients who underwent NIMV or intubated from admission to intensive care, and those who underwent self PP under 12 hours were not included in the study.

The diagnosis of Covid-19 was made by PCR (Polymerase Chain Reaction) test. The diagnosis of pneumonia was made with clinical findings and the presence of multifocal ground-glass opacities that formed consolidation on computed tomography.

Acute respiratory failure; Despite the conventional oxygen treatment applied at 6 lt / min with a reservoir mask, it was defined as the P / F ratio being less than 300.

The first group (EPP) created for our study was composed of patients who received PP at least 12 hours early (with the first 48 hours) with the oxygen support of the reservoir mask, and the

second group (non-EPP) patients who received oxygen with the reservoir mask but could not be applied early PP due to the patient's incompatibility or rejection.

The demographic data of all patients, gender, body mass index (BMI) and additional diseases (Diabetes Mellitus, hypertension, coronary artery disease, Chronic Obstructive Pulmonary Disease, Congestive heart failure, Chronic kidney failure, etc.) were recorded.

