Conventional oxygen therapy applied to all patients was given with a reservoir mask, aiming at SpO₂ 93% and above, at a flow rate of 6-15 L / min. Despite all the treatments, the patients who have a follow-up with a respiratory acidosis (Ph<7,30 and PaCO₂>50 mmhg), SpO₂ value below 93%, applied NIMV, in case of insufficient patient intubated and have invasive mechanical ventilation. In patients who had regression of GKS during follow-up, orotracheal intubation was performed and invasive mechanical ventilation was performed. The number of patients in need of intubation and the number of days they were separated from the ventilator were recorded.

The duration of hospitalization and short-term mortalities of all patients were recorded. Short-term mortality; ICU hospitalization and post-ICU service hospitalization or death up to 28 days in patients discharged home.

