The Effect of Early Prone Position on Prognosis in
Acute Respiratory Failure Due to COVID-19
Pneumonia

05.06.2020

Statistical Analysis:

The data were evaluated using the Windows SPSS 22 package program. Descriptive findings number and percentage distributions for categorical variables; numerical variables are given as mean and standard deviation.

As statistical analysis, Mann-Whitney U test was used for categorical variables, chi-square, normal distribution conditions for numerical variables, Kolmogorov-Smirnov, histogram, and Q – Q Plots graph. Significance level was accepted as $p < 0.05$.

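### Hospital stay is recorded for all patients with no rule for death, so a raw comparison between groups would count an early death as a short stay; the ventilator-days measure has a similar gap

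*Protocol*

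**What the plan says.** The outcome paragraphs of the protocol (unnumbered) state: "The duration of hospitalization and short-term mortalities of all patients were recorded". No start or end of stay is given, and nothing is said about patients who die or are still in hospital when data collection ends. For ventilation the protocol states: "The number of patients in need of intubation and the number of days they were separated from the ventilator were recorded". The only time window in either document is in the definition of short-term mortality: "ICU hospitalization and post-ICU service hospitalization or death up to 28 days in patients discharged home". It is not applied to stay or to ventilator days.

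Patients enter the study on reservoir-mask oxygen "at the stage of admission to the intensive care unit were included in the study", and two groups are formed: "The first group (EPP) created for our study was composed of patients who received PP at least 12 hours early", against patients in whom early proning could not be applied.

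In the SAP, "numerical variables are given as mean and standard deviation". The sentence on tests reads "Mann-Whitney U test was used for categorical variables, chi-square, normal distribution conditions for numerical variables". Its wording is scrambled, but the tests it names are Mann-Whitney and chi-square. No time-to-event, competing-risk or composite method appears, and death is not mentioned.

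**The concern.** Stay can end in two ways, and one of them is death. If both endings enter one column of days, a patient who dies on day 5 looks better than one who goes home on day 18. When the groups have equal mortality this affects both alike and does little harm. When mortality differs, and those who die leave sooner than those who recover, the group with more deaths gets the shorter mean and the lower ranks. Unequal mortality is plausible here: the groups are not randomised, and non-EPP consists of patients who refused or could not comply.

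The ventilator measure has a related gap. The phrase can mean days until separation (fewer is better) or days off the ventilator (more is better). Without a window and a value for death, the direction of any group difference depends on which reading the analyst takes.

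**Working it through.** **No figure to reproduce.** The documents give no sample size, mortality, mean stay or SD. Every input below is an assumption, chosen to show direction and range.

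**1. Mean stay.** For a group with mortality p, mean stay = p × L_d + (1 − p) × L_s, where L_d and L_s are the mean stays of those who die and those who survive. Stays are taken as lognormal with log-SD 0.5, so mean = median × exp(0.125) = median × 1.133. Survivors have a median of 18 d in both groups, so L_s = 20.4 d. Mortality is 40% v 20%.

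| Median time to death | L_d | Mean stay, 40% mortality | Mean stay, 20% mortality |
|---|---|---|---|
| 8 d | 9.1 | 0.4×9.1 + 0.6×20.4 = 15.9 | 0.2×9.1 + 0.8×20.4 = 18.1 |
| 12 d | 13.6 | 17.7 | 19.0 |
| 18 d | 20.4 | 20.4 | 20.4 |
| 22 d | 24.9 | 22.2 | 21.3 |

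Survivors' stay is identical in the two groups, so the whole difference comes from the deaths. Its sign follows the timing of death.

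**2. Mann-Whitney on raw stay.** Same distributions, two-sided p < 0.05, 4,000 simulated studies per cell (standard error at most 0.8 points). Entries are the share of studies in which the higher-mortality group has a significantly shorter stay; chance alone gives about 2.5%.

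| n per group, mortality | Deaths at 8 d | 12 d | 15 d | 18 d | 22 d |
|---|---|---|---|---|---|
| 50, 30% v 20% | 9.8% | 5.6% | 3.5% | 2.7% | 1.8% |
| 50, 40% v 20% | 24.9% | 11.4% | 5.0% | 2.2% | 1.3% |
| 100, 30% v 20% | 14.3% | 8.2% | 4.0% | 2.5% | 1.5% |
| 100, 40% v 20% | 46.1% | 19.3% | 6.8% | 2.5% | 0.6% |

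Repeat runs agree within simulation error; the last row at 8 d came out between 44% and 47%. At 22 d the higher-mortality group is significantly longer in 4–8% of studies, which is the reversal.

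A separate simulation used gamma-distributed stays (survivor mean 20 d, 50 per group, 40% v 20% mortality). It gave 34% with a mean time to death of 6 d and 20% with 10 d. With equal mortality (30% in both groups) it stayed near 2.5%.

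**3. Would the mortality result warn the reader?** Mortality was tested by uncorrected chi-square in the same simulated studies.
- Deaths at 8 d: among studies with a misleading stay result, mortality is non-significant in 27–41% at 30% v 20%, and in 3–11% at 40% v 20%.
- Misleading stay together with non-significant mortality, as a share of all studies: 1.4–4.0% (8 d) and 0.9–3.5% (12 d), or roughly 1–5% allowing for simulation error.

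**4. Stay with death ranked worst.** The wrong direction is significant in at most 0.3% of studies in every scenario. Time to live discharge with deaths kept in the risk set gives at most 0.2%. This removes the wrong sign; it adds no evidence on stay, because survivors' stay was simulated as equal.

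**5. Ventilator measure.** Assumed for intubated patients: 40% v 60% die on the ventilator; median time on it is 12 d in survivors (mean 13.6) and 8 d in those who die (mean 9.1). All figures are means.
- Days on the ventilator, death ending the count: 0.4×9.1 + 0.6×13.6 = 11.8 v 0.6×9.1 + 0.4×13.6 = 10.9. This favours the group with more deaths.
- Days until separation, survivors only: 13.6 v 13.6. No difference.
- Days off to day 28, death scored 0. Survivors average 14.7 (28 minus ventilator days, floored at 0), so 0.6×14.7 = 8.8 v 0.4×14.7 = 5.9. This favours the group with fewer deaths.

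**The case against.** The best reply is that the documents only say that duration was recorded. Neither names stay as an endpoint or says it is compared between groups. That is correct, and the point is conditional on such a comparison. Still, a study of prognosis with two groups, a recorded number of days and a Mann-Whitney test makes it the natural analysis, and nothing written would stop it from being run on raw days.

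The second reply is that mortality is recorded for all patients, so a reader would see the imbalance. This largely stands when the mortality gap is large, and it is why the unflagged harm is only about 1–5% of studies. Seeing the imbalance does not correct the stay comparison, however.

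The third is that the size rests wholly on assumed timing of death. That also stands. What the documents establish is the missing rule, not its effect.

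Some stronger inferences are not supported:
- **That choosing ICU or hospital stay reverses the result.** The boundary of stay is open, but with deaths at 8 d and 40% v 20% mortality, ICU stay (survivor median assumed 8 d) merely shows no difference: median 8.0 v 8.0. With deaths at 12 d the two definitions do point opposite ways (hospital 15.3 v 16.7, ICU 9.4 v 8.6), but only on that assumed ICU median.
- **That days off the ventilator would favour the group with more deaths.** This requires crediting days after death as days off. On a plain reading, a patient who dies while ventilated has no days off.
- **That non-invasive ventilation is probably mixed into the count.** The protocol places it before intubation ("applied NIMV, in case of insufficient patient intubated and have invasive mechanical ventilation"), but the ventilator sentence follows on from intubated patients, so invasive ventilation is the likelier meaning. This and the wording of the mortality definition are matters of missing detail.

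**Conclusion.** The concern holds in conditional form. Stay is recorded for all patients, the SAP has no method that treats death differently from discharge, and a raw comparison of EPP with non-EPP would therefore let early deaths count as short stays. The bias needs both unequal mortality and a difference in timing between deaths and discharges.

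On the assumed inputs it ranges from large (about 10–47% of studies misleading with deaths at 8 d) through modest (6–19% at 12 d) to none (2–3% at 18 d), and it reverses at 22 d. A reader might infer that the study's stay result is biased against EPP. The documents do not show that, since they give neither the mortality nor the timing of death.

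The ventilator point is secondary: the phrase is undefined, and its direction depends on the reading and the death rule.

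The plan should be changed, but this ranks below the mortality comparison, because both are recorded measures reported beside it.

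**What to change.** **Stay.** Measure from ICU admission, the point of inclusion for both groups, to live hospital discharge. Compare groups by time to live discharge with death as a competing event: keep deaths in the risk set, and censor patients still in hospital at data cut-off. Mann-Whitney with death before discharge given the worst rank is a simpler alternative, but only if every patient is followed to discharge or death. Report the result beside mortality, with survivors' stay as descriptive only.

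**Ventilator measure.** Use days alive and off invasive ventilation in a fixed 28-day window, with death by day 28 scored 0. There are two options:
- Start the window at intubation and report it in intubated patients as descriptive, because that subgroup forms after exposure and the groups within it need not be comparable.
- Start it at ICU admission in all patients and label it a composite, since it then differs from the measure recorded.

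**Cost.** SAP wording and re-analysis, with no new patients. Dates of discharge, death, intubation and extubation are needed, so some records may have to be re-abstracted. Worst rank loses power when mortality is equal: with 30% mortality in both groups, deaths at 8 d and survivors' median stay 14 v 18 d, it detects the difference in about 22% of studies at n = 50 (39% at n = 100), against 34% (57%) for raw stay. The change does not replace the plain mortality comparison. Nor does it address the separate issue that EPP status is known only after proning within the first 48 hours.

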The Effect of Early Prone Position on Prognosis in
Acute Respiratory Failure Due to COVID-19
Pneumonia

05.06.2020

Statistical Analysis:

The data were evaluated using the Windows SPSS 22 package program. Descriptive findings number and percentage distributions for categorical variables; numerical variables are given as mean and standard deviation.

As statistical analysis, Mann-Whitney U test was used for categorical variables, chi-square, normal distribution conditions for numerical variables, Kolmogorov-Smirnov, histogram, and Q – Q Plots graph. Significance level was accepted as $p < 0.05$.

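### Only unadjusted two-group tests are planned for a retrospective comparison whose controls refused or could not tolerate early proning

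*SAP*

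**What the plan says.** - **Design.** The opening paragraph of the Protocol says the study was "planned retrospectively in 5 Covid Cohort intensive care units" of one hospital, covering 15.03.2020 to 15.05.2020. There is no randomisation.
- **Aim.** The title of both documents begins "The Effect of Early Prone Position on Prognosis in", which is a causal question.
- **Groups (Protocol, group definitions).** EPP patients had at least 12 hours of proning within the first 48 hours, on a reservoir mask. Non-EPP patients had the mask, but proning "could not be applied early PP due to the patient's incompatibility or rejection".
- **Exclusions (Protocol).** Severity is limited at entry by excluding "P / F ratio below 150, Glaskow Coma Score (GKS) below 12 points, hemodynamic instability", respiratory acidosis, and NIMV or intubation from ICU admission. Acute respiratory failure is defined as P/F below 300. In addition, "those who underwent self PP under 12 hours were not included in the study".
- **Data recorded (Protocol).** "The demographic data of all patients, gender, body mass index (BMI) and additional diseases". No role in the analysis is given to these variables.
- **Outcomes (Protocol).** Need for intubation, days to separation from the ventilator, duration of hospitalisation, and mortality up to 28 days.
- **Analysis (SAP, Statistical Analysis).** Descriptive statistics, normality checks, a 0.05 significance level, and this on testing: "As statistical analysis, Mann-Whitney U test was used for categorical variables, chi-square". The sentence is garbled about which test serves which type of variable. On either reading, both tests are crude two-group comparisons.

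**The concern.** The rule that places a patient in the control group is itself a patient characteristic. Someone who refuses proning or cannot comply may also be more breathless, more agitated, older, heavier or more comorbid, or may simply feel well enough to decline. The term incompatibility is not defined, so it could reflect clinical state, preference or both. Any of these can affect intubation and death independently of proning.

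There is a second selection, made after admission. Membership of EPP requires 12 completed hours of proning, and patients with fewer hours are dropped. As written, a patient who starts proning but is intubated or dies before 12 hours cannot count in EPP, and no matching time or survival condition is stated for controls.

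The plan has no step that addresses either problem. The crude comparison could show a benefit that does not exist or hide one that does, and a reader would have no means of telling which. It is the only between-group analysis planned, so every outcome is affected.

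**Working it through.** **Text check.** The SAP's single section and the whole Protocol were read for regression, propensity score, matching, weighting, stratification, sensitivity analysis or confidence intervals. None appears, and no redaction falls where one would be.

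**What the entry limits do.** P/F from 150 to just under 300 and GCS from 12 upward remain eligible in both groups. Age is limited only to over 18. BMI is not limited, and comorbidity is limited only through the exclusion of other primary pulmonary disease. The limits narrow severity but do not balance it within the permitted range.

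**Illustration of size.** The documents state no sample size, event rate, effect size or allocation ratio, so there is no figure of the plan's to reproduce, and every input below is an assumption. Suppose proning has no effect. A binary severity marker multiplies mortality by *R* and is present in a share *p1* of EPP and *p0* of non-EPP. Then

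crude RR = (1 + *p1*(*R* − 1)) / (1 + *p0*(*R* − 1))

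| *p1* v *p0* | *R* = 2 | *R* = 3 |
|---|---|---|
| 0.3 v 0.5 | 1.3/1.5 = 0.867 | 1.6/2.0 = 0.800 |
| 0.3 v 0.4 | 1.3/1.4 = 0.929 | 1.6/1.8 = 0.889 |
| 0.5 v 0.3 (reversed) | 1.5/1.3 = 1.154 | 2.0/1.6 = 1.250 |

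**Masking.** If the true risk ratio were 0.80 at both levels of the marker and the imbalance were reversed, the crude value would be 0.80 × 1.154 = 0.92 or 0.80 × 1.250 = 1.00.

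**False-positive rate.** Group risk = *m*(1 + *p*(*R* − 1)), where *m* is mortality without the marker. The table gives the exact binomial probability that an uncorrected two-sided chi-square reaches p < 0.05 with equal groups and no true effect.

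| *m* | *R* | Shares | Risks, EPP v non-EPP | 50 per group | 100 | 200 |
|---|---|---|---|---|---|---|
| 20% | 2 | 30% v 50% | 26% v 30% | 7.3% | 9.7% | 14.5% |
| 20% | 3 | 30% v 50% | 32% v 40% | 13.2% | 21.7% | 38.7% |
| 10% | 2 | 30% v 50% | 13% v 15% | 6.5% | 7.0% | 8.9% |
| 10% | 3 | 30% v 50% | 16% v 20% | 8.6% | 11.6% | 18.3% |
| 20% | 2 | 30% v 40% | 26% v 28% | 5.6% | 6.1% | 7.4% |
| 20% | 3 | 30% v 40% | 32% v 36% | 6.9% | 9.2% | 13.6% |
| 10% | 2 | 30% v 40% | 13% v 14% | 5.7% | 5.6% | 6.0% |
| 10% | 3 | 30% v 40% | 16% v 18% | 6.3% | 6.8% | 8.5% |

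With equal risks in the two groups, the same calculation gives about 5% (4.8% to 5.5%). Under imbalance the excess generally grows with sample size, because a larger study estimates the biased difference more precisely.

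**The case against.** The strongest reply is that restriction already does part of the work. The entry criteria remove the sickest patients on oxygenation, consciousness, acidosis and haemodynamics, so a residual marker that triples mortality and splits 30% v 50% may be more than the permitted range allows. Under the milder 30% v 40% split, most rejection rates lie close to 5%, and the 38.7% figure is the extreme of the grid. This is a fair limit on the size: the calculation shows that bias is possible, not that it is present. It does not answer the point about age, BMI and comorbidity, which are largely unrestricted, or about cooperation, which defines the groups.

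Three further replies have some force:

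- A protocol and SAP would not contain baseline results, and a baseline table may be intended, given the planned descriptive statistics. That is reasonable, but describing or testing balance does not adjust for imbalance.
- Adjustment for baseline covariates cannot remove selection by cooperation or by completed hours. This is correct, and it is why those two belong in the limitations. It is not a reason to leave the measurable confounders unadjusted.
- The causal word occurs only in the title, so rewording would meet part of the complaint. It would, but an unadjusted association would still be hard to interpret.

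**Conclusion.** The concern holds and should be fixed before any conclusion about proning is drawn. Followed as written, the plan gives a crude comparison of patients who completed proning with patients who refused it or could not comply, and that does not answer the question in the title. This conclusion rests on the text alone.

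The size of the bias does not follow from the text. Neither the presence nor the direction of a severity imbalance can be known from these documents. Under the assumptions shown, a null effect would appear as a crude risk ratio anywhere from 0.80 to 1.25, and the nominal 5% test would reject in between 5.6% and 38.7% of studies, depending on the imbalance, the strength of the marker, mortality and sample size.

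**What to change.** 1. In the SAP, make the main comparison of intubation and of 28-day mortality an adjusted estimate with a 95% CI, by regression or propensity score. Fix the covariates before outcomes are compared between groups, and keep the model small if events are few.
2. Draw covariates from the recorded demographics (including age and sex), BMI and comorbidities. Add admission P/F, PaCO2 and GCS from the charts used to apply eligibility, and ICU unit where available.
3. Report baseline balance between the groups, and keep the chi-square and Mann-Whitney tests as descriptive.
4. Word the title and conclusions as an association.
5. State as limitations that cooperation defines the exposure and that the 12-hour requirement selects patients after admission, and that baseline adjustment removes neither. Report how many patients were left out for fewer than 12 hours of proning, if the charts allow.

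**Cost.** SAP wording and one added analysis, with no new patients or procedures. P/F, PaCO2, GCS and ICU unit are not in the Protocol's list of recorded data, so some return to charts may be needed. Intervals will be somewhat wider and residual confounding will remain. With no sample size or event count in the documents, the number of covariates the data can support is unknown.
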